15.3 Fluorouracil (Adrucil, Efudex, [5-FU])

- Refer to package insert for complete, up-to-date information.

15.31 Background: Antineoplastic Agent, Antimetabolite (Pyrimidine Analog). Fluorouracil is a fluorinated Pyrimidine Antimetabolite that inhibits thymidylate synthetase, blocking the methylation of deoxyuridylic acid to thymidylic acid, interfering with DNA, and to a lesser degree, RNA synthesis. Fluorouracil appears to be phase specific for the G₁ and S phases of the cell cycle.

15.32 Formulation: Commercially available for injection 50 mg/mL (10 mL, 20 mL, 50 mL, and 100 mL).

15.33 Preparation, storage, and stability: Store intact vials at room temperature and protect from light. A slight discoloration may occur with storage but usually does not denote decomposition. Dilute in 50 – 1000 mL of 0.9% NaCl or D5W. If exposed to cold, a precipitate may form; gentle heating to 60°C will dissolve the precipitate without impairing the potency. Solutions in 50 – 1000 mL 0.9% NaCl or D5W or undiluted solutions in syringes are stable for 72 hours at room temperature. Fluorouracil should not be coadministered with either diazepam, doxorubicin, daunorubicin, idarubicin, cisplatin, or cytarabine. However, fluorouracil and leucovorin are compatible for 14 days at room temperature. Fluorouracil is compatible with vincristine, methotrexate, and cyclophosphamide.

15.34 Administration: Fluorouracil will be given by continuous IV infusion over 46 hours.
Refer to section 7.0 (treatment) administration instructions specific to the protocol.

15.35 Pharmacokinetic information:
Distribution: V_d ~ 22% of total body water; penetrates extracellular fluid, CSF, and third space fluids (e.g., pleural effusions and ascitic fluid)
Metabolism: Hepatic (90%); via a dehydrogenase enzyme; Fluorouracil must be metabolized to be active.
Half-life elimination: Biphasic: Initial: 6-20 minutes; two metabolites, FdUMP and FUTP, have prolonged half-lives depending on the type of tissue.
Excretion: Lung (large amounts as CO₂); urine (5% as unchanged drug) in 6 hours.

15.36 Potential Drug Interactions: Fluorouracil may increase effects of warfarin. Avoid ethanol (due to GI irritation). Avoid black cohosh.

15.37 Known potential adverse events: Consult the package insert for the most current and complete information.

Common known potential toxicities, > 10%:

Dermatologic: Dermatitis, pruritic maculopapular rash, alopecia.
Gastrointestinal (route and schedule dependent): Heartburn, nausea, vomiting, anorexia, stomatitis, esophagitis, anorexia, diarrhea. GI toxicity (anorexia, nausea, and vomiting) is generally more severe with continuous-infusion schedules.
Emetic potential: <1000 mg: Moderately low (10% to 30%) ≥ 1000 mg: Moderate (30% to 60%)
Hematologic: Leukopenia; Myelosuppressive (tends to be more pronounced in patients receiving bolus dosing of FU). Decreased white blood cell count with increased risk of infection; decreased platelet count with increased risk of bleeding.
Local: Irritant chemotherapy.

Less common known potential toxicities, 1% - 10%:

Dermatologic: Dry skin
Gastrointestinal: GI ulceration

Rare known potential toxicities, <1% (Limited to important or life-threatening):

Cardiac enzyme abnormalities, chest pain, coagulopathy, dyspnea, ECG changes similar to ischemic changes, hepatotoxicity; hyperpigmentation of nail beds, face, hands, and veins used in infusion; hypotension, palmar-plantar syndrome (hand-foot syndrome), photosensitization. Cerebellar ataxia, headache, somnolence, ataxia are seen primarily in intracarotid arterial infusions for head and neck tumors.

15.38 **Drug procurement:** Commercial supplies. Each participating ACCRU treating location shall obtain supplies from normal commercial supply chain or wholesaler.

Outdated or remaining drug is to be destroyed on-site as per procedures in place at each institution.

15.39 **Nursing Guidelines:**

15.391 Monitor complete blood count and platelet count. Instruct patient to report signs and symptoms of infection, unusual bruising or bleeding to the physician.

15.392 Administer antiemetics as indicated.

15.393 Diarrhea may be dose-limiting; encourage fluids and treat symptomatically.

15.394 Assess for stomatitis; oral care measures as indicated. May try Vitamin E oil dabbed on sore, six times daily. Cryotherapy recommended with IV push administration.

15.395 Monitor for neurologic symptoms (headache, ataxia).

15.396 Inform patient of potential alopecia.

15.397 Those patients on continuous infusion may need instruction regarding central intravenous catheters and portable intravenous or intra-arterial infusion devices.

15.398 Fluorouracil-induced conjunctivitis is a common problem. Advise patient to report any eye soreness or redness to the healthcare team.

15.399 Photosensitivity may occur. Instruct patients to wear sun block when outdoors.

15.4 Leucovorin Calcium (CF)

- Refer to package insert for complete, up-to-date information.

15.41 **Background:** A reduced form of folic acid, leucovorin supplies the necessary cofactor blocked by methotrexate, enters the cells via the same active transport system as methotrexate. Stabilizes the binding of 5-dUMP and thymidylate synthetase, enhancing the activity of fluorouracil.

15.42 **Formulation:** Commercially available as:

Injection, powder for reconstitution: 50 mg, 100 mg, 200 mg, 350 mg
Injection, solution: 10 mg/mL (10mL, 30 mL)

15.43 **Preparation, storage, and stability:**

Powder for injection: Store at room temperature, protect from light.
Reconstitute with sterile water for injection or bacteriostatic water for injection; dilute in 100-1000 mL 0.9% NaCl or D₅W. When doses > 10 mg/m² are required, reconstitute using sterile water for injection, not a solution containing benzyl alcohol. Solutions reconstituted with bacteriostatic water for injection must be used within 7 days. Solutions reconstituted with sterile water for injection must be used immediately.
Parenteral admixture is stable for 24 hours stored at room temperature and for 4 days when stored under refrigeration.

Solution for injection: Prior to dilution, store vials under refrigeration, protect from light.

15.44 **Administration:** Due to calcium content, do not administer I.V. solutions at a rate > 160 mg/minute. Refer to individual protocols for specific administration instructions.

In combination with irinotecan: Leucovorin is compatible with irinotecan via Y-site injection.³

Leucovorin should be administered I.V. push or I.V. infusion over 30 minutes following irinotecan liposome

In combination with fluorouracil: The fluorouracil is usually given after the leucovorin infusion. Leucovorin is usually administered by I.V. bolus injection or short (10-120 minutes) I.V. infusion, however, in this trial will be given over 30 minutes. Other administration schedules have been used; refer to the treatment section of the protocol for specific directions.

15.45 Pharmacokinetic information:

Metabolism: Intestinal mucosa and hepatically to 5-methyl-tetrahydrofolate (5MTHF; active)

Half-life elimination: ~4-8 hours

Time to peak: I.V.: Total folates: 10 minutes; 5MTHF: ~1 hour

Excretion: Urine (primarily); feces

15.46 Potential Drug Interactions:

Decreased Effect: May decrease efficacy of trimethoprim/sulfamethoxazole against *Pneumocystis carinii* pneumonia.

15.47 Known potential adverse events: Consult the package insert for the most current and complete information.**Frequency not defined:**

Dermatologic: Erythema, pruritis, skin rash, urticarial

Hematologic & oncologic: Thrombocytopenia

Hypersensitivity: Anaphylactoid reaction, hypersensitivity reaction

Respiratory: Wheezing

15.48 Drug procurement: Commercial supplies. Pharmacies or clinics shall obtain supplies from normal commercial supply chain or wholesaler.

Outdated or remaining drug is to be destroyed on-site as per procedures in place at each institution.

15.49 Nursing Guidelines

- 15.491 Headache may occur. Advise patient that analgesics such as Tylenol may help. Instruct patient to report any headache that is unrelieved.
- 15.492 Observe for sensitization reaction (rash, hives, pruritis, facial flushing, and wheezing).
- 15.493 May potentiate the toxic effects of fluropyrimidine (5-FU) therapy, resulting in increased hematologic and gastrointestinal (diarrhea, stomatitis) adverse effects. Monitor closely.
- 15.494 May cause mild nausea or upset stomach. Administer antiemetics if necessary and evaluate for their effectiveness.
- 15.495 If Leucovorin is being used as rescue for high dose methotrexate, does must be given on time. Impress this to the patient. If patient is taking oral Leucovorin at home and is unable to take secondary to nausea, instruct patient to notify the health care team immediately to arrange for other methods of administration.

16.0 Statistical Considerations and Methodology

16.1 Overview

This is a phase I/Ib/II study of the nal-IRI/5FU with rucaparib (MRF) combination.

The phase I portion of this study is a 3+3 trial designed to establish the recommended dose level of the nal-IRI/5FU with rucaparib combination in patients with pancreatic and gastroesophageal cancers (up to 2 lines of prior therapy), colorectal cancer (up to 3 lines of prior therapy), and biliary tract cancer (up to 1 line of prior therapy).

The phase Ib portion of this study is designed to assess, in a preliminary fashion, antitumor efficacy of the recommended dose level of MFR in patients with metastatic disease from pancreatic adenocarcinoma who have received no more than 1 line of prior therapy in the metastatic setting. The recommended dose level determined in the phase I portion of the trial will be used for the Phase Ib portion.

The phase II portion of this study will use a 2-stage Simon design with interim analysis to assess the efficacy of MFR in patients with (untreated) metastatic pancreatic cancer and BRCA1, BRCA2, or PALB2 mutation. The recommended dose level determined in the phase I portion of the trial will be used for the Phase II portion.

16.11 Primary Objective and Endpoint

Phase I: the primary objective is to determine the recommended dose level of the combination MFT nal-IRI/5FU with rucaparib. The end point to this objective is to evaluate the incidence of dose-limiting toxicities (DLT) of nal-IRI/5FU with rucaparib.

Phase Ib: the primary objective is to evaluate, in a preliminary fashion, antitumor efficacy and tolerability of the recommended dose level of MFR in patients with metastatic disease from pancreatic adenocarcinoma who have received no more than 1 line of prior therapy in the metastatic setting. The endpoint to this objective is Disease control (DC) rate which is defined to be RECIST (v 1.1) complete response, partial response, or stable disease, for at least 24 weeks from initiation of study therapy. The purpose of this Phase Ib expansion is to better understand the DC rate and appropriate patient population in order to plan a Phase II trial.

Specimens will be collected at baseline in all patients, and at 16 weeks in patients with disease control at that time.

A portion of the patients will be selected to have known homologous recombination (HR) defects, and approximately 25% of the remaining patients are expected to have HR defects.

Phase II: the primary objective is to estimate the proportion of evaluable patients who reach CR/PR, per RECIST 1.1, ≤ 32 weeks after registration. Evaluable is defined as patients with HRD encompassing BRCA1, BRCA2, and PALB2 deleterious mutations (germline and somatic), consented, eligible, and received any protocol treatment. The end point to this objective is to evaluate changes in size of target lesions according to RECIST 1.1

16.12 Sample Size

The phase I portion of this study is expected to require a minimum of 49 patients and a maximum of 58 patients including 40 patients who will be accrued into the expanded phase Ib cohort (see below).

The phase Ib portion of this trial consists of 2 expansion cohorts of patients adenocarcinoma who have received no more than 1 line of prior therapy in the metastatic setting. The objective of the phase Ib study is exploratory and hypothesis generating in nature. The phase 1b analysis is not powered; thus, no sample sizes were derived. We plan to enroll 40 patients to the Phase Ib, including 28 patients with either unknown mutation status or non-HRD (known wildtype for BRCA1, BRCA2, and PALB2 genes) and 12 patients with known HR deficiency (known mutation in either BRCA1, BRCA2, or PALB2 genes) with the intent of establishing the efficacy of rucaparib in combination with nal-IRI. In addition to 12 patients with known HR deficiency due to mutations in BRCA1, BRCA2, or PALB2, we expect that 7 of 28 Unknown/Non-HRD cohort patients will have HR deficiency since 25% of PDAC patients have defects in DNA repair.

The phase II portion of this study is expected to require a minimum of 11 and a maximum of 21 untreated pancreatic patients with HRD encompassing BRCA1, BRCA2, or PALB2 deleterious mutations (germline and somatic). An additional 3 patients with untreated pancreatic cancer and with BRCA1, BRCA2 or PALB2 deleterious mutation will be accrued to account for ineligibility, cancellation, major treatment violation, or other reasons. We anticipate accruing patients with

other HRD (other than BRCA1, BRCA2, or PALB2) during the phase II portion of the trial for exploratory analysis. Therefore, the phase II portion is expected to screen 200 patients and accrue 24 patients with HRD encompassing BRCA1, BRCA2 and PALB2 patients and another 28 patients with other HRD with an overall sample size will be a maximum of 52 patients.

16.13 Accrual Rate and Study Duration

The anticipated accrual rate for Phase I is 1 patient per month. At this rate, it will likely take about 4 months to enroll, treat, and evaluate each set of 3 patients in the phase I portion of this study. The phase I portion is expected to take between 12 and 24 months.

The anticipated accrual rate for Phase Ib is 3-4 pancreatic cancer patients per month. The phase Ib portion is expected to take up to 20 months.

The anticipated screening rate for Phase II portion is approximately 8-10 patients per month. The anticipated accrual rate for Phase II is approximately 1-2 patients per month for patients with untreated pancreatic cancer with HRD encompassing BRCA1, BRCA2 and PALB2 patients. Therefore, the accrual period is expected to be between 12 and 24 months, depending upon whether the trial will continue accruing patients beyond the interim analysis.

The total study duration is expected to be approximately 24 to 48 months until the last patient accrued in the Phase II portion has been observed for at least 4 months.

16.2 Phase I portion:

The phase I portion of this trial is a single arm phase I study utilizing cohort-of-3 design to determine the recommended dose level of the combination of nal-IRI and 5FU with rucaparib (MFR) in patients with metastatic disease from pancreatic cancer (up to 2 lines of prior therapy), colorectal cancer (up to 3 lines of prior therapy), gastroesophageal cancer (up to 1 line of prior therapy) and biliary tract cancer (BTC; up to 1 line of prior therapy allowed).

Decisions regarding the reopening of the cohort to new patients, the expansion of any other cohort, and the need to dose reduce patients already receiving treatment at the dose level in question will be made by the Study Chair(s).

All patients meeting the eligibility criteria who have signed a consent form and have received one dose of MFR will be included in the analysis. Patients removed from the study during cycle 1 for reasons other than toxicity maybe replaced.

16.21 MTD Definition: Maximum Tolerated Dose (MTD) is defined as the dose level below the lowest dose that induces dose-limiting toxicity (DLT) in at least one-third of patients (at least 2 of a maximum of 6 new patients). A total of 6 patients treated at the MTD will be sufficient to identify common toxicities at the MTD. For instance, those toxicities with an incidence of at least 25% will be observed with a probability of at least 82% (1-(1-0.25)⁶). section 7.42 for DLT definitions.

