16.41 Primary Endpoint

The primary endpoint for the phase II portion of the trial will be the best response rate at 32 weeks, which is defined as the number of patients who had response ≤ 32 weeks of registration divided by the number of evaluable patients. Response is defined as either complete response (CR) or partial response (PR), per RECIST 1.1.

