16.43 Phase II Analysis Plan

16.431 Primary Endpoint Analysis - Estimation: The proportion of best response ≤ 32 weeks will be estimated by the number of evaluable patients who reach CR/PR, per RECIST 1.1, ≤ 32 weeks since registration divided by the total number of evaluable patients. Confidence intervals for the proportion will be calculated according to the approach of Duffy and Santner (1987).

16.432 Secondary Endpoint Analyses

16.432a Overall survival: Survival time is defined as the time from registration to death due to any cause. Patients who fail to return for evaluation after beginning therapy will be censored for survival on the last day of therapy or date last known to be alive, whichever is later. The distribution of survival time will be estimated using the method of Kaplan-Meier (1958).

16.432b Progression-free survival: Progression-free survival is defined as the time from registration to the earliest date documentation of disease progression or death due to any cause. Patients who fail to return for evaluation after beginning therapy will be censored for progression on the last day of therapy or date last known to be alive, whichever is later. The distribution of progression-free

survival will be estimated using the method of Kaplan-Meier (1958).

16.432c Toxicity: As per NCI CTCAE version 4.03, the term toxicity is defined as adverse events that are classified as either “possibly,” “probably,” or “definitely related” to study treatment. The maximum grade for each type of toxicity will be recorded for each patient, and frequency tables will be reviewed to determine toxicity patterns within patient groups. In addition, we will review all adverse event data that is graded as 3, 4, or 5 and classified as either “unrelated” or “unlikely to be related” to study treatment in the event of an actual relationship developing. Adverse events and toxicities will be evaluated using all patients who have received any study treatment as well as summarizing those who have been included in the efficacy analyses. The overall adverse event rates for grade 3 or higher adverse events will be compared using Chi-Square or Fisher’s Exact tests between the two treatment groups.

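### Section 16.13 plans to 4 months of Phase II observation for a 32-week primary endpoint, its 24-48 month total has no room for follow-up or Phase Ib, and the scan and endpoint clocks start on different days

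*Combined protocol and SAP*

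**What the plan says.** On duration, section 16.13 states: "The total study duration is expected to be approximately 24 to 48 months", running "until the last patient accrued in the Phase II portion has been observed for at least 4 months". The components in the same section are:

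- Phase I: "The phase I portion is expected to take between 12 and 24 months".
- Phase Ib: "The phase Ib portion is expected to take up to 20 months".
- Phase II: "the accrual period is expected to be between 12 and 24 months".

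Section 16.11 gives the purpose of Phase Ib as "to better understand the DC rate and appropriate patient population in order to plan a Phase II trial". Section 7.5 makes Phase II depend on Phase I and a discussion with the co-sponsors, and does not mention Phase Ib.

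On the endpoint, section 16.41 counts "the number of patients who had response ≤ 32 weeks of registration", and the estimator in 16.43 counts evaluable patients "who reach CR/PR, per RECIST 1.1, ≤ 32 weeks since registration". The stage 1 stopping rule in 16.421 has a 16-week limit, also from registration.

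On assessments, sections 4.0 and 18.1 place scans before cycle 3 and each later odd cycle until progression. Cycles last 28 days and visits may vary by up to 4 days. Section 6.44 lets treatment start up to 21 days after registration. Section 11.1 asks for re-evaluation every 8 weeks without naming a starting day, and 11.33 asks for a further scan 8 weeks after a first CR or PR.

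**The concern.** Two things do not fit together.

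First, the only statement of minimum observation for the last Phase II patient covers the 16-week stage 1 look but about half of the primary endpoint window. No section says that the final primary analysis waits for week 32. The duration total looks too short even on the section's own terms, which matters for funding, drug supply and the expected reporting date.

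Second, the nominal week-32 scan is tied to treatment start and the 32-week limit to registration. A response first seen at that scan may or may not count, depending on how soon treatment began and when the scan was booked. The decision needs 8 responders among 21 patients, so a single response could matter. The second scan has the same problem at the 16-week limit.

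**Working it through.** A month is taken as 365.25/12 = 30.44 days.

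**1. Observation against endpoint.**
- Planned minimum: 4 × 30.44 / 7 = 17.4 weeks.
- Stage 1 limit: 16 weeks = 112 days = 3.7 months, which is covered.
- Primary endpoint: 32 weeks = 224 days = 7.36 months, which is not covered. The gap is 32 − 17.4 = 14.6 weeks, or 3.36 months.

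**2. Reproducing the stated total.**
- Phase I: section 16.12 gives 49-58 patients including 40 in Phase Ib, so 9-18 in escalation. At about 4 months per set of 3 (16.13), 9/3 × 4 = 12 and 18/3 × 4 = 24 months. Phase Ib therefore cannot sit inside this figure.
- Phase II accrual: 24 patients with BRCA1/2 or PALB2 mutations at 1-2 per month gives 24/2 = 12 and 24/1 = 24 months.
- Sum: 12 + 12 = 24 and 24 + 24 = 48 months. This matches the stated total exactly, with zero months for follow-up and zero for Phase Ib.

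**3. Restated total.**
- With the section's own 4 months: 28-52 months.
- With 32 weeks: 24 + 7.36 = 31.4 to 48 + 7.36 = 55.4 months.
- With Phase Ib in sequence: the lower bound for Phase Ib is 40/4 = 10 months of accrual plus the 24 weeks (5.5 months) that its disease control endpoint needs, giving 15.5 months. The upper bound is the stated 20 months. (At 3 per month, 40/3 + 5.5 = 18.9 months, which fits within 20.) The totals are 12 + 15.5 + 12 + 7.4 = about 47 and 24 + 20 + 24 + 7.4 = about 75 months.

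**4. Scan days from registration.** Day = 56k + start lag (0 to 21) + visit variation (−4 to +4), for scan k centred on day 1 of the next odd cycle, with no cycle delay.

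| Scan | Before cycle | Days from registration | Limit |
|---|---|---|---|
| 1 | 3 | 52-81 | |
| 2 | 5 | 108-137 | 112 (stage 1) |
| 3 | 7 | 164-193 | |
| 4 | 9 | 220-249 | 224 (primary) |

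With a start lag of 5 days or more, the fourth scan is late even at −4 days (224 + 5 − 4 = 225). The third scan stays inside the primary window unless cycle delays exceed 224 − 193 = 31 days. The longest overrun of the fourth scan without cycle delay is 249 − 224 = 25 days, and day 249 is 8.18 months.

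**The case against.** The strongest reply is that section 16.13 is a forecast, not a data cutoff. Its 4 months is a minimum and its total is approximate. Patients are treated and scanned until progression (sections 4.0 and 13.1), the estimator is defined by the 32-week window, and no analysis is scheduled at 4 months. All of this stands. A reader might infer that the last patients will be analysed on about 17 weeks of data, or that follow-up is actually that short. The documents do not support that reading; they show an inconsistent planning sentence.

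That follow-up was left out of the total is also an inference, drawn from the exact sum. It is a strong one, because the parts reproduce both ends of the range. Whether Phase Ib must finish before Phase II is not settled, since 16.11 points one way and 7.5 the other, so both totals are given.

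On the clocks, a limit counted from registration is unambiguous and conservative, and three scans fall inside it unless delays are long. The instruction to scan before the cycle sets no earliest day, so an early booking can still bring the fourth scan within day 224. A reader might infer that the fourth scan always misses, or that power falls by some definite amount. Neither follows. Section 1.3 reports that single-agent rucaparib responses appeared only after cycle 2, but no document gives the share of responses first seen at a fourth scan, so no power loss can be calculated.

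**Conclusion.** The point holds as a minor inconsistency. The observation period in 16.13 is 14.6 weeks short of the primary endpoint window. The 24-48 month total is short by 4 months on its own wording, by about 7.4 months for the 32-week endpoint, and by about 23-27 months if Phase Ib is consecutive (46.9 − 24 and 75.4 − 48).

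Separately, the different starting days can place the fourth scan up to 25 days past the primary limit and the second scan up to 137 − 112 = 25 days past the stage 1 limit. These ranges assume scans centred on day 1 of the odd cycle, the permitted lag and visit window, and no cycle delay; delays would widen them. The effect on the primary endpoint is to lose responses rather than add them, and its size is unknown.

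**What to change.** 1. In 16.13, replace the 4-month figure with follow-up of the last evaluable Phase II patient through the week-32 assessment, and state that the final primary analysis waits for it. Restate total duration as about 31-55 months without Phase Ib, or about 47-75 months if Phase Ib is consecutive, and say which applies.

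2. Put tumor assessments and both the 16-week and 32-week limits on one calendar clock that does not move with cycle delays, and reconcile 11.1 with 4.0 and 18.1. There are two ways:
   - Schedule all scans every 8 weeks from registration, with the week-16 and week-32 scans due by days 112 and 224. This keeps the 8-week spacing in 11.1 and 11.33. Moving only the fourth scan would not.
   - Run scans and both limits from cycle 1 day 1, with the same fixed visit window for each.

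Cost: no extra patients. The final analysis falls 3.4 months (7.36 − 4) to 4.2 months (8.18 − 4) after the stated minimum. Under the registration option, a patient with a 21-day lag has the first scan 56 − 21 = 35 days after starting treatment. Under the cycle 1 day 1 option, the endpoint window lengthens by up to 25 days from registration and the upper totals rise by up to 0.8 month. The sponsor should then confirm that the 23% null rate in 16.42, which is stated without a time limit, still applies.
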